# 6. Statistical Methodology

#### 6.1 Analysis Sets

The ITT analysis set is henceforth referred to as the Full Analysis Set (FAS) and defined as follows:

• Full Analysis Set (FAS): Participants who were randomized within RGB plus placebo participants from specified regimens, classified according to their randomized treatment assignment. Observations made after premature permanent discontinuation of study drug are included in this sample, should such participants remain on study. Observations completed after regimen data lock are excluded. Participants determined to not meet ALS diagnostic criteria are excluded.

The definition of the STF analysis set is revised as follows:

Safety Full (STF) Set: Participants who initiated treatment within RGB plus placebo
participants from specified regimens who are not known to be ineligible for RGB and who
initiated treatment in their respective regimen, classified according to the treatment they
actually received. Observations made after premature permanent discontinuation of study
drug are included in this sample, should such participants remain on study. Observations
completed after regimen data lock are excluded.

An analysis set restricting shared placebo participants to those regimens in which study drug is administered by the same route as RGB is defined as follows:

• Efficacy Common Mode of Administration (ECM) Set: The subset of participants in the FAS analysis set who are in regimens in which study drug is administered by the same route as RGB.

The definitions of the ECC, ERO, STN, and SRO analysis sets are the same as described in the M-SAP with reference to the ITT analysis set now referencing the FAS analysis set. The following analysis set is specific to RGB:

Efficacy Per-protocol (EPP) Set: The subset of participants in the FAS analysis set who initiated study treatment and who were not involved in protocol deviations that affected the scientific integrity of the trial as documented prior to data lock, classified according to the treatment they actually received. Inclusion or exclusion from the EPP analysis set of any participant for whom treatment assignment was unblinded prior to data lock will be governed by the prespecified criteria above. If a participant's data is truncated for inclusion in the EPP analysis set due to non-adherence to protocol-specified dosing, clinical events observed up to 28 days after the censoring event will be included in the EPP analysis set. For all other events leading to truncation of a participant's data, no events beyond that date will be included. Data from placebo participants shared from other regimens will not be truncated due to non-adherence to protocol-specified dosing.

•

Applicable analysis sets (FAS, ECM, EPP, STF, and STN) will include shared placebo participants from regimens A and C only. Data from shared placebo participants will include visits and events that occurred on or before the date of the final placebo-controlled period follow-up of a regimen A, B, or C participant. As only concurrently enrolling regimens are

contributing to efficacy analyses, the FAS and ECC analysis sets are synonymous and only the FAS analysis set will be referenced. As regimen A is administered by subcutaneous injection and regimen C is administered orally, only regimen C will contribute shared placebo participants for the ECM and STN analysis sets.

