| SAE | Serious Adverse Event |

| | |
|-------|---------------------------------|
| SI | Site Investigator |
| SOA | Schedule of Activities |
| SOD | Superoxide dismutase |
| SVC | Slow Vital Capacity |
| T3 | Triiodothyronine |
| T4 | Thyroxine |
| TSPO | Translocator Protein |
| TPO | Thyroid Peroxidase |
| TSH | Thyroid Stimulating Hormone |
| TSPO | Translocator Protein |
| USB | Universal Serial Bus |
| USP | US Pharmacopoeia |
| VC | Vital Capacity |
| WOCBP | Women of Childbearing Potential |

REGIMEN-SPECIFIC APPENDIX (RSA) SUMMARY

Regimen-Specific Appendix [B]

For verdiperstat (also known as BHV-3241).

Rationale and RSA Design

The proposed study is based on cumulative preclinical and clinical studies that implicate myeloperoxidase (MPO) activity in the onset and progression of neurodegenerative diseases and suggest treatment with verdiperstat at a dosage of 600 mg twice daily (BID) has the potential to slow neurodegeneration in Amyotrophic Lateral Sclerosis (ALS).

Allocation to Treatment Regimens

Participants must first be screened under the Master Protocol before they are randomized to an RSA. As soon as pre-defined criteria for futility for the RSA are met, or the target number of randomized participants for the RSA has been reached, enrollment will stop in the RSA.

Number of Planned Participants and Treatment Groups

The number of planned participants for this regimen is approximately 160.

There are 2 treatment groups for this regimen, active and placebo. Participants will be randomized in a 3:1 ratio to active treatment or placebo (i.e., 120 active: 40 placebo).

Planned Number of Sites

Research participants will be enrolled from approximately 60 centers in the US.

Treatment Duration

The maximum duration of the placebo-controlled portion is 24 weeks.

Follow-up Duration

At the conclusion of the 24-week placebo-controlled period of the study, all participants will either schedule a 28-day follow up phone call and end their participation in the regimen or have the option to receive verdiperstat in the open-label extension (OLE) phase of the study.

The OLE portion of the study will continue until verdiperstat is approved and available in the United States, or Biohaven Pharmaceuticals terminates development of verdiperstat for ALS. At the completion of the OLE, a Follow-up Safety Call should be conducted approximately 28 days after the last dose of study drug.

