# 6.3 Primary Efficacy Analysis and Supportive Analyses

The primary analysis for RGB is a Bayesian shared-parameter, repeated-measures model of ALSFRS-R that accounts for loss of follow-up due to mortality. Details of the model, including documentation of operating characteristics under a range of scenarios, are provided in the "ALS Master Protocol Recommended Statistical Analysis, Design and Simulation Report" (Appendix 1 to the Master Protocol). The Bayesian shared-parameter, repeated-measures model will be applied to the FAS analysis set as the primary analysis, to the ECM and ERO analysis sets as sensitivity analyses, and to the EPP analysis sets as a supportive analysis.

The estimand of the primary analysis is the relative rate of disease progression (the "disease rate ratio" or DRR) of active treatment relative to placebo in the FAS population under an assumption that active treatment slows mean time to death or death equivalent by the same proportion as treatment slows the mean rate of functional progression as measured by change in ALSFRS-R total score over time. The estimand is defined by the following attributes:

- Treatment: verdiperstat administered orally at a dosage of 600 mg BID vs. placebo.
- Population: FAS population as defined in Section 6.1.
- Variables: time to death or death equivalent and rate of change in ALSFRS-R total score from baseline to the Week 24 Visit.
- Intercurrent event 1: treatment discontinuation due to death: no ALSFRS-R data from participants who reach the death or death equivalent endpoint are included in the analysis, handled via mortality component in model, composite variable strategy approach.
- Intercurrent event 2: treatment discontinuation not due to death: handled via treatment policy approach, all data will be used including data collected during the placebo-controlled period after treatment discontinuation regardless of concomitant medication, for those participants who have not been censored due to mortality. Missing data post-treatment will not be imputed, handled via missing at random assumption.
- Population-level summary: mean ratio of hazard or progression rate of active treatment relative to placebo.

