# 6.5 Secondary Efficacy Analyses

# 6.5.1 Hierarchical Testing

Primary inference for secondary efficacy endpoints will be based on analysis of the FAS analysis set using a repeated-measures linear mixed model for functional endpoints (see Section 6.5.2 below) and by Kaplan-Meier product-limit estimates and log-rank test for the primary survival endpoint (see Section 6.5.4 below). The sequence for testing secondary efficacy endpoints is the following:

- 1. HHD upper extremity percentage,
- 2. SVC,
- 3. HHD lower extremity percentage, and
- 4. Survival.

If the primary analysis indicates a significant slowing in disease progression from the Bayesian shared-parameter, repeated-measures model of ALSFRS-R and mortality, then each secondary efficacy endpoint in succession would be declared significant in the specified sequence using a comparison-wise criterion of two-tailed p < 0.05. After the first failure to declare significance, no endpoints lower in the hierarchy can be significant. This sequential closed-testing procedure controls the overall type 1 error rate at 5%. Nominal comparison-wise p-values for secondary efficacy endpoints will also be reported.

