#### 6.5.4 Survival and Time to Clinical Events

Survival and time to hospitalizations and clinical events will be analyzed in the FAS, ECM, ERO, EPP, STF, SFN, and SRO analysis sets. Survival analyses that include follow-up beyond the placebo-controlled period will be analyzed in the ERO analysis set. The summaries and analyses of time to death or death equivalent are the same as specified in the M-SAP with the revision to include baseline age as an additional covariate in adjusted models, with the addition that the endpoints of time to death independent of occurrence of death equivalents and time to each of the hospitalization and clinical events will be separately analyzed using the same models, and with an additional adjusted analysis that includes baseline serum NfL level as a covariate. Analysis of time to King's stage 4a or 4b will accommodate interval censoring between ALSFRS-R assessments and will be stratified by baseline King's stage.

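### The supportive per-protocol set can truncate Regimen B data for dosing non-adherence but exempts shared placebo; one companion Regimen B-only run would show the result under a single rule

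*SAP*

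**What the plan says.** SAP 6.1 defines one EPP set, specific to this regimen, as a subset of the FAS. It includes placebo participants shared from Regimens A and C. Three statements matter:

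- Dosing non-adherence can shorten a participant's record: "If a participant's data is truncated for inclusion in the EPP analysis set due to non-adherence to protocol-specified dosing", then "clinical events observed up to 28 days after the censoring event will be included in the EPP analysis set".
- Shared placebo is exempt from that rule: "Data from placebo participants shared from other regimens will not be truncated due to non-adherence to protocol-specified dosing". No such exemption is stated for other causes of truncation.
- Regimen B itself is randomised 3:1 ("i.e., 120 active: 40 placebo", Protocol RSA Summary).

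SAP 6.3 applies the Bayesian model to the FAS as primary analysis, "to the ECM and ERO analysis sets as sensitivity analyses", and "to the EPP analysis sets as a supportive analysis". ERO is the regimen-only set; ECM limits shared placebo to regimens with the same route of administration. SAP 6.5.4 also uses EPP: "Survival and time to hospitalizations and clinical events will be analyzed in the FAS, ECM, ERO, EPP, STF, SFN, and SRO analysis sets". For the secondary endpoints, SAP 6.5.1 says: "Primary inference for secondary efficacy endpoints will be based on analysis of the FAS analysis set".

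The SAP revision history lists the exemption among the version 3.0 changes, so it is deliberate. No reason is given. No EPP set limited to Regimen B is defined.

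**The concern.** Truncating data for dosing behaviour selects on something that happens after randomisation. When one rule covers both arms and non-adherence is similar in each, the selection largely cancels. Here it need not: the later course of non-adherent participants can be removed throughout the active arm but is kept for most of the controls if Regimens A and C together share more than 40.

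The EPP result will be read beside the FAS result. The two share nearly all their data, so most of the noise cancels in the difference between them. A modest artefact could then look like an on-treatment effect. ERO and ECM are not per-protocol sets, and the comparison of controls across regimens (SAP 6.5.11) compares placebo groups with each other. No planned run gives a per-protocol estimate under one rule.

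**Working it through.** **1. Who faces the rule.** 160 x 3/4 = 120 active and 160 x 1/4 = 40 placebo, as the protocol states. Let S be the number of shared placebo participants, which the documents do not give. The exempt fraction of the control arm is S/(40+S): 50% for S = 40, 67% for S = 80, 71% for S = 100. In the active arm it is 0%.

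**2. A yardstick for size.** Protocol 10.1 sets success at a posterior probability above 98.0%, treated here as one-sided alpha 0.02 (z = 2.054). Protocol Table 10.2.2 gives power 0.615, 0.776 and 0.888 for 25%, 30% and 35% slowing. With SE = slowing/(z_power + 2.054):

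- 0.25/(0.292 + 2.054) = 0.1066
- 0.30/(0.759 + 2.054) = 0.1067
- 0.35/(1.216 + 2.054) = 0.1070

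The mean, 0.1068, returns powers of 0.613, 0.775 and 0.890, close to those stated. The protocol's own figures therefore imply an SE of about 11 points of percent slowing. This is a calibration, because the simulation report is not among the documents.

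**3. Null simulation.** This is not the Bayesian model. ALSFRS-R is measured at weeks 0, 4, 8, 12, 16, 20 and 24 (SAP 2.9), with 120 active and 40 Regimen B placebo. Assumed: 80 shared placebo, mean slope -1.0 per month (SD 0.8), intercept SD 5, residual SD 1.8, equal non-adherence in both arms. Analysis: random-slopes model with treatment and treatment-by-month, 1500 runs per setting. The model SE is 0.115-0.119 per month, or about 12 points on a slope of 1.0, near the yardstick in step 2.

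Mean EPP-minus-FAS gap in points of percent slowing (positive favours active):

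| Stopping depends on | Decline after stopping | 5% | 10% | 15% | 25% |
|---|---|---|---|---|---|
| chance | unchanged | 0.1 | 0.0 | 0.0 | 0.0 |
| observed decline | unchanged | 0.1 | 0.1 | 0.0 | 0.0 |
| true slope | unchanged | 1.3 | 2.5 | 3.8 | 6.3 |
| chance | 1.5 times as fast | 0.8 | 1.6 | 2.5 | 4.4 |
| observed decline | 1.5 times as fast | 1.2 | 2.3 | 3.3 | 5.7 |
| true slope | 1.5 times as fast | 2.6 | 5.4 | 7.7 | 12.6 |
| chance | half as fast | -0.8 | -1.7 | -2.7 | -4.9 |
| observed decline | half as fast | -1.2 | -2.4 | -3.7 | -6.9 |
| true slope | half as fast | -0.3 | -0.6 | -0.9 | -1.4 |

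Monte Carlo SEs are 0.03 to 0.14. For true-slope stopping with decline unchanged, the SD of the gap is 1.9, 2.5, 3.1 and 3.9. A separately written simulation with a somewhat stronger link gave 3.2 at 10% and 4.8 at 15%. In the last row it gave values near zero (0.1 to 0.5), so there even the sign depends on the assumed link.

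**4. Size in context.** At 10% and 15%, true slope, decline unchanged: 2.5/12 = 0.21 and 3.8/12 = 0.32 of the EPP standard error, but about 1.0 and 1.2 times the SD of the gap (2.5/2.5 and 3.8/3.1).

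**5. What a companion run would do.** With equal non-adherence, Regimen B-only EPP minus ERO lies between -0.35 and +0.22 in all 36 settings. Three limits apply:

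- Precision: SE ratio = sqrt[(1/40 + 1/120)/(1/(40+S) + 1/120)] = 1.26, 1.41 and 1.47 for S = 40, 80 and 100. The simulated SE rises to 0.163-0.173.
- Noise: for true-slope stopping with decline unchanged, the SD of the companion gap is 5.3 at 15%, above the 3.8-point bias it would check.
- Unequal non-adherence: at 20% active and 10% placebo (true slope, decline unchanged) the companion gap is still 3.2, against 5.8 as written. A second simulation gave 4.2 for the companion.

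Replacing the current run would lower total error only if the bias exceeded sqrt(0.163² - 0.115²) = 0.116 to sqrt(0.173² - 0.119²) = 0.126, about 12 points. One of the 36 settings did.

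**6. Survival.** At 5% mortality (Protocol Table 10.2.3 base, read as 24-week), 15% non-adherence and S = 80, the false hazard ratio is 1.00 if stopping and death are unlinked, 0.97 if they share a cause or hazard doubles after stopping, and 1.02 if it halves. Expected deaths are about 240 x 0.05 = 12, so SE(log HR) is about sqrt(4/12) = 0.58, against |log 0.97| = 0.03.

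**The case against.** The strongest reply is that nothing turns on EPP. It is supportive, no success rule attaches to it, and the SAP sets no rule for reading an EPP-FAS difference. This stands and keeps the point minor.

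Second, the bias comes from assumed mechanisms. The progression-linked stop in the protocol is loss of swallowing (Protocol 5.5). Swallowing is a bulbar function (Protocol 7.3) and the ALSFRS-R has a bulbar domain (SAP 5.10), so observed scores should capture much of that decline. In the matching setting the gap is at most 0.1 if decline is unchanged. The SAP gives no threshold for dosing non-adherence, and down-titration, drug holidays and stopping on loss of swallowing are all provided for in the protocol and may not count. This stands as a limit on size. It does not remove the unequal rule.

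Third, the companion run is noisy and is clean only if non-adherence is similar in the two Regimen B arms. This stands too: it is a reason to add the run with its limits stated and not to substitute it.

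A reader might infer that EPP is tilted towards verdiperstat. The documents do not support that: the gap is near zero in some settings and negative in others. A reader might also infer that the survival and clinical-event results need the same treatment. For survival, the illustrated distortion is a small fraction of its standard error.

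**Conclusion.** The unequal rule is in the text, and no planned analysis gives a per-protocol result under one rule. The supportive EPP disease rate ratio can be biased if non-adherence carries prognostic information beyond the observed scores, or if decline changes after stopping. Direction and size cannot be fixed from the documents.

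The headline range of about 2.5 to 4 points at 10-15% rests on the assumed slopes, 80 shared placebo participants, equal non-adherence in both arms and stopping driven by true slope with decline unchanged. That is a fifth to a third of the EPP standard error.

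This is an inexpensive improvement to consider. It is not a flaw in the trial's inference: the FAS primary analysis, the ERO and ECM runs and the hierarchical secondary tests do not use the rule.

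**What to change.** Keep the exemption and the current EPP run. Before unblinding:

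- In SAP 6.1 and 6.3, add one companion run of the Bayesian model on the EPP subset of ERO. Read it beside the planned ERO run, and the current EPP run beside FAS, so that each difference compares like with like.
- Next to the listing in SAP 6.7.1, report by arm the number of participants truncated for dosing non-adherence. SAP 6.7.2 (compliance, interruptions, dose reductions) and 6.7.6 (deviations by type and group) cover related summaries but not this count.
- State the limits: an interval about 1.4 times as wide if 80 placebo participants are shared, a noisy companion gap, and a remaining gap if non-adherence is more frequent on active drug (about 3 points at 20% versus 10% in simulation). The companion removes only the distortion from unequal rules.

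The cost is two or three sentences, one supportive run and one count, using Regimen B dosing data already being summarised. Extending the companion to SAP 6.5.4 should be optional at most. It would add runs for two survival definitions and six clinical-event endpoints, with adjusted and NfL-adjusted models, for little information.

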# 6.2 Baseline Characterization

The baseline characteristics summarized for participants randomized within RGB are the same as specified in the M-SAP with the addition of ALSAQ-40 domain scores and SI, CNS-BFS total score, King's stage, weight, body mass index (BMI), serum urate concentration, serum creatinine concentration, and serum NfL concentration.

# 6.3 Primary Efficacy Analysis and Supportive Analyses

The primary analysis for RGB is a Bayesian shared-parameter, repeated-measures model of ALSFRS-R that accounts for loss of follow-up due to mortality. Details of the model, including documentation of operating characteristics under a range of scenarios, are provided in the "ALS Master Protocol Recommended Statistical Analysis, Design and Simulation Report" (Appendix 1 to the Master Protocol). The Bayesian shared-parameter, repeated-measures model will be applied to the FAS analysis set as the primary analysis, to the ECM and ERO analysis sets as sensitivity analyses, and to the EPP analysis sets as a supportive analysis.

The estimand of the primary analysis is the relative rate of disease progression (the "disease rate ratio" or DRR) of active treatment relative to placebo in the FAS population under an assumption that active treatment slows mean time to death or death equivalent by the same proportion as treatment slows the mean rate of functional progression as measured by change in ALSFRS-R total score over time. The estimand is defined by the following attributes:

- Treatment: verdiperstat administered orally at a dosage of 600 mg BID vs. placebo.
- Population: FAS population as defined in Section 6.1.
- Variables: time to death or death equivalent and rate of change in ALSFRS-R total score from baseline to the Week 24 Visit.
- Intercurrent event 1: treatment discontinuation due to death: no ALSFRS-R data from participants who reach the death or death equivalent endpoint are included in the analysis, handled via mortality component in model, composite variable strategy approach.
- Intercurrent event 2: treatment discontinuation not due to death: handled via treatment policy approach, all data will be used including data collected during the placebo-controlled period after treatment discontinuation regardless of concomitant medication, for those participants who have not been censored due to mortality. Missing data post-treatment will not be imputed, handled via missing at random assumption.
- Population-level summary: mean ratio of hazard or progression rate of active treatment relative to placebo.

### 6.4 Interim Analysis

RGB will be considered for early stopping for futility according to the interim analysis schedule and definition specified in the "ALS Master Protocol Recommended Statistical Analysis, Design

and Simulation Report" (Appendix 1 to the Master Protocol). RGB will not be stopped early for success.

# 6.5 Secondary Efficacy Analyses

# 6.5.1 Hierarchical Testing

Primary inference for secondary efficacy endpoints will be based on analysis of the FAS analysis set using a repeated-measures linear mixed model for functional endpoints (see Section 6.5.2 below) and by Kaplan-Meier product-limit estimates and log-rank test for the primary survival endpoint (see Section 6.5.4 below). The sequence for testing secondary efficacy endpoints is the following:

- 1. HHD upper extremity percentage,
- 2. SVC,
- 3. HHD lower extremity percentage, and
- 4. Survival.

If the primary analysis indicates a significant slowing in disease progression from the Bayesian shared-parameter, repeated-measures model of ALSFRS-R and mortality, then each secondary efficacy endpoint in succession would be declared significant in the specified sequence using a comparison-wise criterion of two-tailed p < 0.05. After the first failure to declare significance, no endpoints lower in the hierarchy can be significant. This sequential closed-testing procedure controls the overall type 1 error rate at 5%. Nominal comparison-wise p-values for secondary efficacy endpoints will also be reported.

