#### 2.5 Regimen Allocation

Participants in RGB are those determined eligible for Master Protocol-level inclusion and exclusion criteria and randomly assigned to RGB, stratified by use of riluzole, edaravone, both, or neither at the time of screening for the Master Protocol. Details of regimen assignment are described in the Platform Trial Regimen Assignment Plan.

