#### 2.6 Treatment Allocation

Participants in RGB are randomly allocated in a 3:1 ratio to active or placebo treatment based on a pre-specified permuted-block randomization schedule, stratified by use of riluzole, edaravone, both, or neither at the time of screening for the Master Protocol.

Page 12 of 13

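### The primary survival log-rank test names no strata, although randomisation is stratified by riluzole and edaravone use; stratifying by that factor is a cheap safeguard

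*SAP*

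**What the plan says.** SAP 6.5.1 bases primary inference for survival in the full analysis set on a test "by Kaplan-Meier product-limit estimates and log-rank test for the primary survival endpoint". It applies a "comparison-wise criterion of two-tailed p < 0.05", and survival comes fourth in a fixed sequence that opens only if the primary endpoint succeeds. No strata are named.

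SAP 6.5.4 takes its survival summaries and analyses over from the Master SAP, "with the revision to include baseline age as an additional covariate in adjusted models". It also adds a model with serum NfL. The Master SAP is not among the documents.

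Background treatment is a randomisation factor at both levels. Participants are "randomly assigned to RGB, stratified by use of riluzole, edaravone, both, or neither at the time of screening" (SAP 2.5). Within the regimen, the 3:1 allocation follows a "pre-specified permuted-block randomization schedule, stratified by use of riluzole, edaravone, both, or neither" (SAP 2.6).

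The analysis set "will include shared placebo participants from regimens A and C only" (SAP 6.1), in addition to the regimen's own placebo participants.

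The repeated-measures model in SAP 6.5.2, which tests the three functional endpoints ahead of survival, has riluzole and edaravone terms and a random effect for regimen.

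**The concern.** Survival is the one endpoint in the hierarchy whose primary test is not shown to account for background treatment, although the trial randomises by it.

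Pooling makes this more than a matter of tidiness. The permuted blocks balance the regimen's own 120 active against its own 40 placebo participants. They do not balance the active arm against placebo participants from regimens A and C. That balance depends on stratified assignment to regimen, which comes before regimen-specific consent and screening (protocol, Schedule of Activities note 5 and 6.1.1). SAP 6.7.1 provides for losses in that interval: screen failure, withdrawal and timing out. Regimen A is injected and regimen C is oral (SAP 6.1), so such losses could differ by regimen.

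If the realised mix differs and the strata are prognostic, the difference enters an unstratified survival comparison directly. It can favour either arm.

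**Working it through.** The plan states no event count or power for survival, so there is no figure of its own to reproduce. The arm sizes check: 160 × 3/4 = 120 and 160 × 1/4 = 40.

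**Inputs from the documents.** 120 verdiperstat and 40 placebo (protocol summary); two-sided 0.05, so 2.5% per side (SAP 6.5.1); mortality 5%, 10% and 20% and mortality hazard ratio 0.70 (protocol Table 10.2.3); follow-up to Week 24 (SAP 5.9).

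**Assumptions.** 40 placebo participants each from A and C, so 120 controls. Mortality is the 24-week placebo risk (the period is not stated). In the 4,000-trial runs reported in Steps 2, 4 and 5 and in the last two rows of Step 3, the shares of neither / riluzole only / edaravone only / both are 25/50/5/20%, with 10% dropout. Their stratum hazards are all equal, moderate (1.5/1/1/0.67) or strong (3/1/1/0.33).

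**Step 1: information available.** Events D = 120m + 120[1 − (1 − m)^0.70]. Power = Φ(√(D × 0.25) × |ln 0.70| − 1.96).

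- m = 5%: D = 6.0 + 4.2 = 10.2; power 8.2%
- m = 10%: D = 12.0 + 8.5 = 20.5; power 12.5%
- m = 20%: D = 24.0 + 17.4 = 41.4; power 20.8%

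For 80% power, D = (1.96 + 0.842)² / (0.25 × 0.357²) ≈ 247.

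**Step 2: equal mix, no effect.** Error in favour of verdiperstat over all mortality and hazard settings (4,000 trials each, Monte Carlo SE √(0.025 × 0.975/4000) ≈ 0.25 points) is 1.8-2.8% unstratified and 2.1-2.7% stratified. The lowest unstratified value, 1.8%, comes with strong strata at 20% mortality.

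**Step 3: unequal mix, no effect.** Same error; controls compared with the active arm.

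| Shift in controls | Hazards | Mortality | Unstratified | Four-level stratified |
|---|---|---|---|---|
| 5 points more neither, 7.5 fewer both (20,000 trials) | 2- to 4-fold | 10-20% | 3.2-4.5% | 2.2-2.5% |
| Same shift, separate run | prognostic | not itemised | 2.4-4.4% | 2.1-3.0% |
| Same shift reversed (4,000 trials) | 2- and 4-fold | 5-20% | 1.2-2.1% | not tabulated |
| 10 more neither, 15 fewer both (20,000 trials) | 2- to 4-fold | 10-20% | 3.9-7.4% | 2.3-2.6% |
| A and C placebo at 40/45/3/12% (4,000 trials) | moderate | 5-20% | 2.8-3.8% | 2.3-2.5% |
| A and C placebo at 40/45/3/12% (4,000 trials) | strong | 5-20% | 4.2-7.8% | 2.3-2.7% |

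In the last two rows the 15-point shift applies to 80 of 120 controls, so it is 15 × 80/120 = 10 points in the pooled group. The 7.8% needs strong strata, a hazard ratio of about 3/0.33 = 9 between neither and both, and 20% mortality.

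**Step 4: power at hazard ratio 0.70, equal mix, unstratified then stratified.**

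| Mortality | No prognostic effect | Moderate | Strong |
|---|---|---|---|
| 5% | 8.0, 7.9% | 8.2, 8.2% | 7.6, 8.2% |
| 10% | 12.1, 12.1% | 11.5, 11.9% | 10.5, 11.5% |
| 20% | 19.7, 19.6% | 19.0, 19.2% | 16.9, 19.4% |

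The largest loss in these runs, 0.3 points, was at hazard ratio 0.40 (41.0 to 40.7%). In the other runs the change stayed below 1 point either way.

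**Step 5: adding regimen as a stratum.** Regimens A and C have no verdiperstat participants in this analysis, so their strata contribute nothing. The events left are 40m + 120[1 − (1 − m)^0.70] = 6.2, 12.5 and 25.4. With 0.75 × 0.25 in place of 0.25, power is 5.8%, 7.9% and 11.9%. Simulated power with background-by-regimen strata at 20% mortality is 14.5-15.2%, against 16.9-19.7% unstratified.

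**The case against.** Four points deserve weight.

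First, a reader might infer that the plan fixes an unstratified test. It does not say so. The SAP records departures from the Master SAP, and 6.5.4 defers to it, so strata may be defined there. This stands: what can be shown is that the text supplied names none. SAP 6.5.4 does name a stratification factor for the King's stage analysis.

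Second, a reader might infer that the survival comparison is biased. The documents do not support that. Assignment to regimen is random and stratified by the same four levels, controls are concurrent (protocol 10.2), and protocol 10.3 describes only minor eligibility differences. The expected mix is therefore equal. Chance imbalance is already in the test's null distribution: under simple random assignment the unstratified error was 2.2-2.9%. The standard deviation of the difference in the neither share would then be √(2 × 0.25 × 0.75/120) = 5.6 points, and for both √(2 × 0.20 × 0.80/120) = 5.2 points, so a 15-point difference in both is nearly 3 standard deviations. This stands too. Differential loss after assignment remains possible, but no document gives its size.

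Third, covariate-adjusted survival models, own-placebo and same-route analysis sets (SAP 6.5.4) and comparisons of controls across regimens (6.5.11) would help to expose a mix-driven result. They are not the primary inference.

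Fourth, stratification is not strictly free of power cost. That is correct; the cost is small.

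**Conclusion.** The point holds as a low-severity improvement. Bias and inflated error have not been demonstrated. With equal mixes the unstratified test is valid, and mildly conservative if strata are strongly prognostic. If the realised mix differs by an assumed 5 to 15 points and the strata are prognostic, one-sided error is about 2.4-7.8% unstratified against 2.1-3.0% stratified when the shift favours verdiperstat. It falls below nominal when the shift runs the other way.

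These figures rest on assumed stratum shares, hazards, shifts and control numbers, none of which the documents give. The upper end needs an extreme combination.

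The practical stake is limited by survival's place at the end of the hierarchy and its power of about 8-21%. Nominal p-values are to be reported regardless (SAP 6.5.1), so the result will be read even if the sequence stops earlier.

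**What to change.** In SAP 6.5.1 and 6.5.4, state that the primary survival log-rank test is stratified by the four-level background-treatment factor used in randomisation (neither, riluzole only, edaravone only, both, as recorded at Master Protocol screening). State that it is not stratified by regimen, since that would discard the shared controls. Keep the unstratified log-rank test as a sensitivity analysis. If the Master SAP already sets strata, a cross-reference in 6.5.1 is enough.

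The cost is one sentence in the SAP and one added statement in the analysis program, with no new data. The statistical downside is a power loss of under about 1 point if the strata turn out not to be prognostic.
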